### **3.3 Safety Monitoring on Study and Post-Treatment Follow-Up**

Enrollment will begin with a single cohort of three subject slots. No additional enrollment will be permitted until the first three subjects have completed a full treatment schedule (defined as C1D1 of pembrolizumab through the End of Treatment visit). This temporary pause and review of data is to ensure thorough safety monitoring of the first three subjects enrolled. The data will be reviewed to ensure that pembrolizumab in combination with radiation therapy does not increase the toxicity profile of either treatment in a manner that is unexpected or compromises subject safety.

During this initial 3-subject enrollment, if one or more of the three subjects experiences a serious unexpected adverse event at least possibly related to pembrolizumab or radiation treatment, the temporary enrollment hold will be extended as the Sponsor-Investigator evaluates the potential risk and safety. During this enrollment hold, the Sponsor-Investigator will review all currently collected safety data and make an evaluation as to whether to permit further accrual.

If none of the first three subjects experience a serious unexpected adverse event related to pembrolizumab or radiation treatment, enrollment may continue without restriction. If at any point in time there is greater than 30% of subjects who have unexpected, probably related SAEs grade III or higher that do not resolve to grade 2 within 2 weeks, the trial will pause enrollment for safety review by the Sponsor-Investigator.

All subjects will have an End of Treatment visit 30 days ( $\pm$  14 days) after the completion of pembrolizumab therapy, which may coincide with the pre-operative visit. Subjects will have a Wound Care Follow-Up visit 30 days ( $\pm$  14 days) after their first standard of care post-operative visit to determine how the wound healing is proceeding. If there are wound healing complications or any other ongoing toxicities related to treatment at that time, the subject will continue to be monitored until the toxicity/complication resolves, improves to maximal anticipated improvement, or the study closes.

Subjects will be followed for as many as 5 years after completing treatment for survival determination. This may be done via publicly available records, medical record review, or by phone.

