Duration	Record the start and stop dates of the adverse event. If less than 1 day, indicate the appropriate length of time and units						
Action taken	Did the adverse event cause Merck product to be discontinued?						
Relationship to Merck Product	
Did Merck product cause the adverse event? The determination of the likelihood that Merck product caused the adverse event will be provided by an investigator who is a qualified physician. The investigator's signed/dated initials on the source document or worksheet that supports the causality noted on the AE form, ensures that a medically qualified assessment of causality was done. This initialed document must be retained for the required regulatory time frame. The criteria below are intended as reference guidelines to assist the investigator in assessing the likelihood of a relationship between the test drug and the adverse event based upon the available information.
 
The following components are to be used to assess the relationship between Merck product and the AE; the greater the correlation with the components and their respective elements (in number and/or intensity), the more likely Merck product caused the adverse event (AE):
 
 
 Exposure	Is there evidence that the subject was actually exposed to Merck product such as: reliable history, acceptable compliance assessment (pill count, diary, etc.), expected pharmacologic effect, or measurement of drug/metabolite in bodily specimen?	
 
 Time Course	Did the AE follow in a reasonable temporal sequence from administration of Merck product? Is the time of onset of the AE compatible with a drug-induced effect (applies to trials with investigational medicinal product)?	
 
 Likely Cause	Is the AE not reasonably explained by another etiology such as underlying disease, other drug(s)/vaccine(s), or other host or environmental factors	
 
	Exposure	Is there evidence that the subject was actually exposed to Merck product such as: reliable history, acceptable compliance assessment (pill count, diary, etc.), expected pharmacologic effect, or measurement of drug/metabolite in bodily specimen?	Time Course	Did the AE follow in a reasonable temporal sequence from administration of Merck product? Is the time of onset of the AE compatible with a drug-induced effect (applies to trials with investigational medicinal product)?	Likely Cause	Is the AE not reasonably explained by another etiology such as underlying disease, other drug(s)/vaccine(s), or other host or environmental factors

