Exposure	Is there evidence that the subject was actually exposed to Merck product such as: reliable history, acceptable compliance assessment (pill count, diary, etc.), expected pharmacologic effect, or measurement of drug/metabolite in bodily specimen?						
Time Course	Did the AE follow in a reasonable temporal sequence from administration of Merck product? Is the time of onset of the AE compatible with a drug-induced effect (applies to trials with investigational medicinal product)?						
Likely Cause	Is the AE not reasonably explained by another etiology such as underlying disease, other drug(s)/vaccine(s), or other host or environmental factors						

Relationship to Merck Product (continued)	The following components are to be used to assess the relationship between the test drug and the AE: (continued)		
	Dechallenge	
Was Merck product discontinued or dose/exposure/frequency reduced?
 
If yes, did the AE resolve or improve?
 
If yes, this is a positive dechallenge. If no, this is a negative dechallenge.
 
(Note: This criterion is not applicable if: (1) the AE resulted in death or permanent disability; (2) the AE resolved/improved despite continuation of the Sponsor's product; or (3) the trial is a single-dose drug trial); or (4) Sponsor's product(s) is/are only used one time.)
	
	Rechallenge	
Was the subject re-exposed to Merck product in this study?
 
If yes, did the AE recur or worsen?
 
If yes, this is a positive rechallenge. If no, this is a negative rechallenge.
 
(Note: This criterion is not applicable if: (1) the initial AE resulted in death or permanent disability, or (2) the trial is a single-dose drug trial); or (3) Sponsor's product(s) is/are used only one time).
 
NOTE: IF A RECHALLENGE IS PLANNED FOR AN ADVERSE EVENT WHICH WAS SERIOUS AND WHICH MAY HAVE BEEN CAUSED BY MERCK PRODUCT, OR IF REEXPOSURE TO MERCK PRODUCT POSES ADDITIONAL POTENTIAL SIGNIFICANT RISK TO THE SUBJECT, THEN THE RECHALLENGE MUST BE APPROVED IN ADVANCE BY THE SPONSOR AS PER DOSE MODIFICATION GUIDELINES IN THE PROTOCOL.
	
	Consistency with Trial Treatment Profile	Is the clinical/pathological presentation of the AE consistent with previous knowledge regarding Merck product or drug class pharmacology or toxicology?	

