The assessment of relationship will be reported on the case report forms /worksheets by an investigator who is a qualified physician according to his/her best clinical judgment, including consideration of the above elements.			
Record one of the following		Use the following scale of criteria as guidance (not all criteria must be present to be indicative of Merck product relationship).	

Yes, there is a reasonable possibility of Merck product relationship.	There is evidence of exposure to Merck product. The temporal sequence of the AE onset relative to the administration of Merck product is reasonable. The AE is more likely explained by Merck product than by another cause.
No, there is not a reasonable possibility of Merck product relationship	Subject did not receive the Merck product OR temporal sequence of the AE onset relative to administration of Merck product is not reasonable OR the AE is more likely explained by another cause than the Merck product. (Also entered for a subject with overdose without an associated AE.)

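### Do the Section 3.3 safety triggers fail because Table 6 records causality only as Yes/No for the Merck product and expectedness is not a listed attribute?

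*Combined protocol and SAP*

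**What the plan says.** Section 3.3 sets two safety triggers.

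- **First three subjects.** Enrolment stops until all three have finished treatment and their data have been reviewed. The hold is extended if any of them has "a serious unexpected adverse event at least possibly related to pembrolizumab or radiation treatment". The release condition drops the qualifier: "If none of the first three subjects experience a serious unexpected adverse event related to pembrolizumab or radiation treatment", enrolment may go on without restriction.
- **At any time.** Enrolment pauses for review by the Sponsor-Investigator if more than 30% of subjects have "unexpected, probably related SAEs grade III or higher that do not resolve to grade 2 within 2 weeks". This sentence does not say to which treatment the event must be related.

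Section 9.4.1 says that toxicities are characterised by seriousness, causality, grade and action taken. Table 6, placed under Section 9.4.2.2, sets out the causality question: "Did Merck product cause the adverse event". One of two answers is recorded. The positive one is "Yes, there is a reasonable possibility of Merck product relationship", with guidance that includes "The AE is more likely explained by Merck product than by another cause". The guidance for the negative answer includes the case where "the AE is more likely explained by another cause than the Merck product". The nearest item to expectedness is one component of the causality assessment: "Is the clinical/pathological presentation of the AE consistent with previous knowledge regarding Merck product or drug class pharmacology or toxicology".

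**The concern.** The triggers use two levels of relatedness (possible and probable) plus an unqualified form, and two treatments. The recorded item has one level and one treatment. An event that is possibly due to pembrolizumab but more likely due to radiation meets the first-three trigger, yet the Table 6 guidance leans towards No. Both triggers also require the event to be unexpected. Section 3.3 names no reference for that, and Section 9.4.1 does not list it as an attribute to record.

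Safety of the combination is a secondary objective (Section 4.2), and the 30% rule is the only numerical safety trigger after the first three subjects. Section 12.0 has committees look at adverse events and stopping rules. If the data showed neither attribution to radiation, nor the level of relatedness used, nor expectedness, a committee could not reconstruct whether a trigger had been met. If counts were taken mechanically from Table 6, radiation-attributed events would drop out and the pause would come less often.

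**Working it through.** **1. Which trigger elements can be checked from the data as specified?**

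| Element in Section 3.3 | Where it is recorded or judged |
|---|---|
| Serious | Sections 9.4.1 and 9.4.2.1, Table 6 |
| Grade III or higher | CTCAE grade; every grade change is recorded (9.4.2.2) |
| Not down to grade 2 within 2 weeks | grade changes plus start and stop dates (Table 6) |
| Related to pembrolizumab | Table 6, Yes/No |
| Related to radiation | 9.4.1 requires causality without naming a product; no item is spelled out |
| Possibly or probably | no counterpart defined |
| Unexpected | no field; partial sources in 7.3.2 (common radiation toxicities, optional list by the radiation oncologist) and in 6.1 and 6.1.2 (pembrolizumab label) |

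The gap is confined to the last three rows.

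**2. Is Table 6 the source of the counts?** Section 3.3 does not refer to it. The table stands under immediate reporting to the sponsor and to Merck, which explains why it asks only about that product. Section 9.4.1 defines adverse events by association with pembrolizumab and/or radiation, and Table 2 lists radiation as a trial treatment. The eCRF is not part of the documents, so a radiation item may exist.

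**3. Is Table 6 stricter than the first-three trigger?** The label of the positive answer speaks of a reasonable possibility, which is close to possible relatedness. Its guidance speaks of the more likely cause, which is closer to probable. The column heading says that not every criterion has to be present, and the table calls its criteria reference guidelines. The table is therefore ambiguous, and not plainly stricter.

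**4. What if counts were taken from Table 6 alone?** The plan states no event rate and no operating characteristic for the 30% rule, so there is no figure of its own to reproduce. Let p be the per-subject rate of qualifying events due to either treatment, and s the share marked No because radiation is judged the likelier cause. Both are assumptions. The recorded rate is q = p(1 − s).

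The rule trips at the first n where count/n > 0.30. The smallest such counts include 2 of 4, 3 of 7, 4 of 10, 7 of 20 and 8 of 26. With independent subjects evaluated in order of enrolment, the exact recursion is f(n, k) = f(n−1, k)(1 − q) + f(n−1, k−1)q, where paths with k > 0.30n are removed and added up as trips.

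Chance of a trip within 26 subjects, checks from subject 4 (the first three have their own hold):

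| p | s = 0 | s = 25% | s = 50% | s = 75% |
|---|---|---|---|---|
| 1% | 0.15% | 0.08% | 0.04% | 0.01% |
| 2% | 0.6% | 0.3% | 0.15% | 0.04% |
| 5% | 3.5% | 2.0% | 0.9% | 0.2% |
| 10% | 13.4% | 7.8% | 3.5% | 0.9% |
| 20% | 46.7% | 28.5% | 13.4% | 3.5% |
| 30% | 79.7% | 56.0% | 28.5% | 7.8% |

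At p = 5% the largest loss is 3.53 − 0.23 = 3.3 points. At p = 20% and s = 50% it is 46.7 − 13.4 = 33.3 points. With checks from subject 1, the row for p = 5% reads 15.0/11.3/7.5/3.8%. That row is higher mainly because a single event among the first three already exceeds 30%, and those subjects are under a hold anyway.

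The chance that the first-three hold is extended is 1 − (1 − q)³. At p = 10%: 1 − 0.90³ = 27.1% for s = 0, and 1 − 0.95³ = 14.3% for s = 50%. At p = 5% the values are 14.3% and 7.3%.

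**5. What do these figures measure?** They measure counting from a Merck-only item, under the reading that either treatment counts. If relatedness in the 30% sentence means pembrolizumab only, s does not enter. If the Sponsor-Investigator judges each case against Section 3.3, then s = 0 and every difference vanishes. The figures say nothing about expectedness or about possible versus probable. The rows for 20% and 30% also need a very high rate for a conjunction of five conditions (serious, unexpected, probably related, grade III or higher, unresolved at 2 weeks), and the documents give no basis for such a rate.

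**The case for a change.** The strongest case for a change is that judgement belongs in the review that follows a trigger, while the question of whether the trigger was met should be answerable from the data. The protocol describes the combination as never used before in this setting with conventionally fractionated radiation. The first-three review asks about the toxicity of either treatment, yet attribution is spelled out for only one. No text asks for attribution to radiation, defines the two levels of relatedness, or requires expectedness to be recorded. The remedy would cost a few sentences and one or two CRF fields.

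The description of the text stands, and so does the point about traceability. The step from there to a failing trigger does not. A protocol need not write out every CRF field. Within the reporting window of Section 9.4.2.1, serious events go to the Sponsor-Investigator within 24 hours whether or not they are related to the drug, and the same person decides on the pause. The data of the first three subjects are reviewed in any case, so that trigger decides only whether a hold already in force is extended. Section 7.6 allows termination on the incidence or severity of adverse drug reactions, with no test of expectedness and no level of relatedness. Section 13.3 lets the Sponsor-Investigator terminate at any time, and Section 12.0 adds independent monitoring.

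**Conclusion.** The wording of Section 3.3 and of Table 6 does not match, and no reference for expectedness is named. This is a gap in documentation that the people applying the rule can fill sensibly: the Sponsor-Investigator sees the serious events in the reporting window and can judge relatedness to each treatment, and expectedness, case by case. Followed as written, the plan is not shown to miss a review or to produce a wrong result. Safety is tabulated descriptively (Section 10.1), and no endpoint, estimate or power figure depends on the point.

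The numerical effect is nil under case review. It appears only if counts come from the Merck-only item and radiation-attributed events are meant to count. Then, with checks from subject 4, it is at most 3.3 percentage points at assumed event rates of 5% or below, and it becomes large only at rates of 20% to 30%, for which the documents give no support. What remains is easier reconstruction for the review committees, which is a matter of good record keeping. The conclusion rests on the Sponsor-Investigator applying Section 3.3 by its own terms and not through Table 6.

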#### **7.2.1.1.2 Dose Modification and Toxicity Management for Immune-Related AEs Associated with Pembrolizumab and Immuno-oncology (IO) combination partners**

AEs associated with pembrolizumab or IO/IO combination exposure, , may represent an immunologic etiology. These immune-related AEs (irAEs) may occur shortly after the first dose or several months after the last dose of pembrolizumab or combination treatment and may affect more than one body system simultaneously. Therefore, early recognition and initiation of treatment is critical to reduce complications. Based on existing clinical study data, most irAEs were reversible and could be managed with interruptions of pembrolizumab or combination treatment, administration of corticosteroids and/or other supportive care. For suspected irAEs, ensure adequate evaluation to confirm etiology or exclude other causes. Additional procedures or tests such as bronchoscopy, endoscopy, skin biopsy may be included as part of the evaluation. Based on the severity of irAEs, withhold or permanently discontinue pembrolizumab or combination treatment and administer corticosteroids. Dose modification and toxicity management guidelines for irAEs associated with pembrolizumab are provided in Table 3 and Table 6.

**Note:** The treatment guidelines are intended to be applied when the investigator determines the events to be related to pembrolizumab. If after the evaluation the event is determined not to be related to pembrolizumab, the investigator does not need to follow the treatment guidance.

**Table 3 - Dose modification and toxicity management guidelines for immune-related AEs associated with pembrolizumab and IO combination partners**

General instructions:				
Immune-related AEs	Toxicity grade or conditions (CTCAE v5.0)	Action taken to pembrolizumab	irAE management with corticosteroid and/or other therapies	Monitor and follow-up
Pneumonitis	Grade 2	Withhold	
 
Administer corticosteroids (initial dose of 1-2 mg/kg prednisone or equivalent) followed by taper
 
Add prophylactic antibiotics for opportunistic
 
	
 
Monitor participants for signs and symptoms of pneumonitis
 
Evaluate participants with suspected pneumonitis with radiographic imaging and initiate corticosteroid treatment
 

	Recurrent Grade 2, Grade 3 or 4	Permanently discontinue		

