#### **7.2.1.1.3 Dose Modification and Toxicity Management of Infusion-Reactions Related to Pembrolizumab**

Pembrolizumab or other drugs in combination may cause severe or life threatening infusion-reactions including severe hypersensitivity or anaphylaxis. Signs and symptoms usually develop during or shortly after drug infusion and generally resolve completely within 24 hours of completion of infusion. Dose modification and toxicity management guidelines on pembrolizumab associated infusion reaction are provided in Table 4.

Table 4 - Pembrolizumab Infusion-Reaction Dose modification and Treatment Guidelines

NCI CTCAE Grade	Treatment	Premedication at Subsequent Dosing
Grade 1 Mild reaction; infusion interruption not indicated; intervention not indicated	Increase monitoring of vital signs as medically indicated until the participant is deemed medically stable in the opinion of the investigator.	None
Grade 2 Requires therapy or infusion interruption but responds promptly to symptomatic treatment (e.g., antihistamines, NSAIDs, narcotics, IV fluids); prophylactic medications indicated for ≤24 hrs	
Stop Infusion.
 
Additional appropriate medical therapy may include but is not limited to: IV fluids, Antihistamines, NSAIDs, Acetaminophen, Narcotics
 
Increase monitoring of vital signs as medically indicated until the participant is deemed medically stable in the opinion of the investigator.
 
If symptoms resolve within 1 hour of stopping drug infusion, the infusion may be restarted at 50% of the original infusion rate (e.g. from 100 mL/hr to 50 mL/hr).
 
Otherwise dosing will be held until symptoms resolve and the participant should be premedicated for the next scheduled dose.
 
Participants who develop Grade 2 toxicity despite adequate premedication should be permanently discontinued from further study drug treatment
	
Participant may be premedicated 1.5h (± 30 minutes) prior to infusion of _____ with: Diphenhydramine 50 mg po (or equivalent dose of antihistamine). Acetaminophen 500-1000 mg po (or equivalent dose of analgesic).

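### After the first three subjects, the numeric safety pause in section 3.3 does not count Grade 3-4 related SAEs that improve to Grade 2 within 2 weeks; only discretionary review covers them

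*Combined protocol and SAP*

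**What the plan says.** Section 3.3 (Safety Monitoring on Study and Post-Treatment Follow-Up) sets two rules.

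- **Run-in, subjects 1-3.** Enrollment is held until these three have completed treatment. The hold is extended "if one or more of the three subjects experiences a serious unexpected adverse event at least possibly related to pembrolizumab or radiation treatment". There is no minimum grade and no condition on how long the event lasts.
- **Afterwards.** If the run-in is clean, enrollment is unrestricted apart from one numeric trigger, which needs more than 30% of subjects with "unexpected, probably related SAEs grade III or higher that do not resolve to grade 2 within 2 weeks". Crossing that threshold has one stated consequence, namely that "the trial will pause enrollment for safety review by the Sponsor-Investigator".

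Table 6 defines Grade 4 as life-threatening.

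Other provisions bear on the same events without a number and without a resolution condition:

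- Section 9.4.2.1 sends SAEs to the Sponsor-Investigator within 24 hours.
- Section 7.6 lists the frequency or severity of drug reactions as a ground for early termination.
- Section 12.0 provides committee review at least once a year and as needed, with approval required to continue.
- Section 13.3 lets the Sponsor-Investigator terminate at any time, and the FDA may also do so.

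On the usual course of toxicity, section 7.2.1.1.2 says that "most irAEs were reversible and could be managed with interruptions of pembrolizumab or combination treatment", with corticosteroids and supportive care. Of infusion reactions, section 7.2.1.1.3 says: "Signs and symptoms usually develop during or shortly after drug infusion and generally resolve completely within 24 hours of completion of infusion".

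**The concern.** For subjects 4-26 the trigger measures persistence rather than incidence. A life-threatening event that responds to treatment within 14 days leaves no trace in the count, although the need to treat it is itself safety information about a combination that section 3.1 describes as new in this curative setting. The two rules in section 3.3 therefore treat one and the same event differently according to the subject's position in the sequence, and no reason is given.

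There is also a timing effect. An event cannot be known to be unresolved at 2 weeks until 2 weeks have passed, and the section does not say from which date it counts. Enrollment stays open meanwhile.

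**Working it through.** **The plan's own figure.** Section 10.1 gives one safety probability, a 94% chance of observing a toxicity with 10% prevalence in 26 subjects. It reproduces: 1 - 0.90^26 = 0.935. No operating characteristic is given for the pause rule.

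**The threshold.** More than 30% means at least 2 of 4, 2 of 5, 4 of 10, 7 of 20 or 8 of 26.

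**One worked case.** Suppose subjects 1-3 have no event, and subjects 4 and 5 each have an unexpected, probably related Grade 4 SAE that reaches Grade 2 on day 10. If these counted, 2/5 = 40% would exceed 30% and enrollment would pause. Under the clause the count is 0/5. The same event in subject 3 would have extended the run-in hold.

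**Chance of a pause.** Two inputs are assumptions, because the documents give neither:

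- p: the proportion of subjects with an unexpected, probably related Grade 3 or higher SAE
- s: the share of those events still above Grade 2 at 2 weeks

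The counted rate is c = p × s. Let f(n,k) be the probability of k counted subjects among the first n with no pause so far. With a clean run-in, f(3,0) = 1. For n = 4 to 26:

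f(n,k) = f(n-1,k) × (1 - c) + f(n-1,k-1) × c

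Any probability with k/n > 0.30 is moved to the paused state. Subjects are independent, each is counted once, outcomes are known at once, and the denominator is subjects enrolled so far (section 3.3 does not define it).

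Probability of a pause, given a clean run-in:

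| p | s = 1 | s = 0.75 | s = 0.50 | s = 0.25 | s = 0 |
|---|---|---|---|---|---|
| 20% | 0.244 | 0.119 | 0.044 | 0.009 | 0 |
| 30% | 0.589 | 0.323 | 0.119 | 0.022 | 0 |
| 40% | 0.866 | 0.589 | 0.244 | 0.044 | 0 |
| 50% | 0.977 | 0.813 | 0.410 | 0.075 | 0 |

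The s = 1 column is also what the rule would give if every event counted whatever its duration. At s = 0 the result is zero for any p.

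**Including the run-in.** A clean run-in has probability (1 - p)^3: 0.512 at p = 20% and 0.6^3 = 0.216 at p = 40%. The chance that neither rule acts is (1 - p)^3 × (1 - table entry).

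- p = 40%: 0.216 × (1 - 0.866) = 0.03 at s = 1, and 0.216 × (1 - 0.044) = 0.21 at s = 0.25.
- p = 20%: 0.512 × (1 - 0.244) = 0.39 at s = 1, and 0.512 × (1 - 0.009) = 0.51 at s = 0.25.

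**Counting Grade 4 events whatever their duration.** With a clean run-in and every event resolving in time, the same recursion with c equal to the Grade 4 rate gives 0.044, 0.119 and 0.244 at Grade 4 rates of 10%, 15% and 20%. Under the present clause all three are zero.

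**The case against.** A reader might infer that repeated, treatable life-threatening toxicity can never pause enrollment. The documents do not support that. Sections 7.6, 12.0 and 13.3 allow the trial to be stopped on the frequency or severity of reactions, by committee decision or at the Sponsor-Investigator's discretion, and section 9.4.2.1 brings SAEs to the Sponsor-Investigator within 24 hours whether or not they resolve. This stands. What these routes lack is a threshold. They are mostly framed as termination or approval to continue, and committee review is guaranteed only yearly against an estimated 12-month enrollment (section 1.0).

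The large contrasts in the table also depend on a clean run-in, which at p = 40% happens only 22% of the time. Otherwise the run-in hold is extended and a review takes place, although accrual may then resume. Rates of 40-50% for events that are both unexpected and probably related are high, and the figures cover all Grade 3 or higher events, not Grade 4 alone. All of this stands, and it limits how far the numbers should be pressed.

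A strict run-in followed by a rule aimed at persistent toxicity is a recognisable design, not an outright contradiction. Nor do the statements on immune-related and infusion reactions show that most qualifying events would resolve within 2 weeks. The former gives no time frame, and many such reactions may be classed as expected and so fall outside the rule anyway. They make the exclusion plausible in practice but do not quantify it.

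**Conclusion.** The point holds in a limited form. After the first three subjects, no prespecified numeric rule in section 3.3 pauses enrollment for unexpected, probably related Grade 3-4 SAEs that improve to Grade 2 within 2 weeks, whatever their number. That follows from the text and needs no assumption. Deaths are not affected by the clause, since a Grade 5 event cannot resolve.

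How much the clause weakens the trigger depends on two unknown rates. Given a clean run-in and p = 40%, the chance of a pause drops from 0.87 to 0.24 when half the events persist and to 0.04 when a quarter do. Counting the run-in as well, the chance that neither rule acts rises from 0.03 to 0.21 over the same span from s = 1 to s = 0.25. The conclusion is that a prespecified trigger is missing for these events, not that the trial cannot be stopped. It is a cheap improvement to a safety rule.

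**What to change.** Reconcile the two rules in section 3.3:

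1. Word the later pause so that it does not disregard life-threatening (Grade 4) unexpected related SAEs solely because they improved within 2 weeks.
2. State from what date an event counts.
3. Report the rule's chance of pausing with and without the resolution clause, including the run-in, over a stated range of event and persistence rates, and give the reason for the clause that is kept.

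This narrows the mismatch with the run-in rule but does not remove it. The run-in acts on a single event of any grade that is at least possibly related, whereas the later rule would still need more than 30% of subjects and a probable relationship. One Grade 4 event in subject 4 would still be only 1/4 = 25%.

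The cost is about a sentence in section 3.3 and a short table in section 10.1. No new data are needed, because grade changes and start and stop dates are already recorded (section 9.4.2.2 and Table 6). The downside is a somewhat higher chance of a temporary enrollment pause for review, of the order shown in the last step of the working. The change concerns enrollment only, not any subject's treatment.
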